#### 8.4.2 Imaging Analysis

Quantitative gamma SPECT/CT will be performed over the chest and abdomen of the patient at specified timepoints after intra-arterial administration of 99mTc-MAA. Absorbed dose in units of mGy/GBq for each organ of interest and total absorbed dose within the imaged area will be calculated using a 510(k) cleared software product. Mean absorbed doses ± standard deviation for each region of interest will be calculated for the study population.

### 8.5 Early Withdrawal/Premature Discontinuation of Subjects

Subjects may be withdrawn early from the study for several reasons including:

- Subject death
- Subject request for withdrawal (withdrawal of consent)

- Adverse event
- Investigator decision

If a subject is withdrawn from the study early, a Study Completion CRF must be completed to describe the reason for early withdrawal. In situations where study withdrawal is due to an adverse event, subjects will be followed until resolution of the adverse event or determination that the subject's condition is stable.

If a subject chooses to withdraw from the study and also withdraws consent for disclosure of further information, no further study assessments should be performed and no additional data collected. The sponsor may retain and continue to use any data collected prior to the withdrawal of consent.

### **8.5.1 Subject Replacement**

If a subject is withdrawn prior to the 24-hour follow-up, they will be replaced. Subject numbering will proceed as described in **Section 8.2**.

## **9.0 STATISTICAL METHODS**

### **9.1 Analysis Data Sets**

The primary analysis will consist of all available data on all subjects enrolled, referred to in International Conference on Harmonisation (ICH) E9 Statistical Principles for Clinical Trials as the full analysis set. As the study is a treatment-only, single arm design, comparisons between treatment and control groups are not pertinent, and summaries of results will principally be presented for the entire study population.

### **9.2 General Principles**

Continuous data will be summarized using the following descriptive statistics: mean, standard deviation, median, and range or interquartile range. Categorical variables will be summarized using frequency counts and percentages. For events that can occur more than once in a single subject, such as AEs, the percentage will be based on the number of subjects experiencing the event; both subject and event counts will be reported.

All statistical analyses will be performed using SAS (version 9.4 or higher, SAS Institute Inc. Cary, NC), R (version 3.2 or higher, R Foundation for Statistical Computing, Vienna, Austria) or other widely accepted statistical or graphical software.

### **9.3 Analysis of Primary Endpoints**

The primary endpoints are defined in **Section 6.1** and will be presented descriptively under the general principles cited above. Summary statistics for each endpoint will be reported at each of the three timepoints at which they are measured, thereby obtaining activity (GBq) and dose (Gy) over time related to 99mTc-MAA as part of SIRT planning. As the study is nonrandomized, summary statistics of primary interest are those for the enrolled population as a whole and

evaluation of subgroups is not planned *a priori* and no hypothesis testing against predefined null hypotheses or between subgroups is expected.

#### **9.4 Safety Analysis**

An overall summary of severe adverse events (AEs, grade  $\geq 3$ ) that occur over the 24-hour period of the study will be presented. The summary will include the number and percentage of subjects with at least one AE and the total number of AEs. Complete subject listings of all site-reported AEs will be provided.

AEs will additionally be classified according to Common Terminology Criteria for Adverse Events (CTCAE) v5.0 terms, summarized by severity, relationship to the  $^{99m}\text{Tc}$ -MAA study, outcome, and seriousness. Serious adverse events (SAEs) will be summarized according to severity and relationship. Multiple occurrences of the same AE are counted once at the maximum grade.

### **10.0 MEASURES TO AVOID & MINIMIZE BIAS**

The study has several measures that have been implemented to avoid and minimize bias, including use of an independent CRO for study operations management, monitoring, and data management.

### **11.0 BENEFITS & RISK ANALYSIS**

#### **11.1 Potential Benefits of Study Participation**

There are no guaranteed benefits from participation in this study. There is no obligation for a patient to take part in this study. As an alternative to participation, patients may choose to receive standard of care mapping procedures while being evaluated for SIR-Spheres eligibility.

#### **11.2 Potential Risks Associated with Study Participation**

Risks associated with  $^{99m}\text{Tc}$ -MAA mapping procedure will be listed in the site's procedure consent form used per their standard of care.

Two non-standard of care SPECT/CT scans will be conducted for this study, which involves additional exposure to ionizing radiation. Ionizing radiation exposure risks include a very small increase in the likelihood that a person exposed to radiation will develop cancer later in life. However, the doses used in CT examinations are 10 to 100 times lower than the dose levels that have been reported to increase the risk of cancer (McCollough).

#### **11.3 Methods to Minimize Risks**

$^{99m}\text{Tc}$ -MAA is a well-known and well characterized radiopharmaceutical. Only authorized users with training and licensure per 10 CFR 35.290 can order  $^{99m}\text{Tc}$  as a radioisotope to be used for imaging and localization.

In addition, risks will be further minimized through careful subject screening and selection, training of investigators and study staff, adherence to the scheduled assessments, and regular monitoring visits.

## 12.0 ADVERSE EVENTS

### 12.1 Adverse Event Definitions

Adverse events (AEs) will be adjudicated for severity, seriousness, and for relatedness to the m99Tc-MAA drug and m99Tc-MAA procedure. Refer to **Section 14.0** for AE definitions.

### 12.2 Adverse Event Collection & Documentation

Collection of AEs will start on the day of the procedure for enrolled subjects and will be assessed and reported throughout the study. Investigators must obtain all information available to determine the seriousness, relatedness, and outcome of the adverse event. All AEs will be followed until resolution or investigator determination that the subject's condition is stable.

All reported AEs will be documented on the AE eCRF. Copies of de-identified source documentation that contain significant information related to the event (e.g., progress notes, consultations, nurse's notes, operative reports, subject summaries) may be requested by the sponsor and CRO as needed for evaluation.

The following are not considered AEs for this study:

- Any condition that is recorded as pre-existing on the Baseline eCRF, unless there is a worsening of that condition in terms of nature, severity, or degree of incidence.
- Planned hospitalization for pre-existing conditions or a procedure required by the protocol, without serious deterioration in health.
- AEs arising from vascular access (e.g., hematoma, pseudoaneurysm, etc.), catheter selection (e.g., rupture, dissection, thrombosis).

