## 14.0 DEFINITIONS

**Adverse drug reaction (ADR):** In the pre-approval clinical experience with a new medicinal product or its new usages, particularly as the therapeutic dose(s) may not be established, all noxious and unintended responses to a medicinal product related to any dose should be considered adverse drug reactions. The phrase "responses to a medicinal product" means that a causal relationship between a medicinal product and an adverse event is at least a reasonable possibility (i.e., the relationship cannot be ruled out). (ICH E6 (R2), 1.1)

- Note regarding marketed medicinal products: A response to a drug which is noxious and unintended, and which occurs at doses normally used in man for prophylaxis, diagnosis, or therapy of diseases or for modification of physiological function.

**Adverse event (AE):** Any untoward medical occurrence in a patient or clinical investigation subject administered a pharmaceutical product and which does not necessarily have a causal relationship with this treatment. An AE can therefore be any unfavorable and unintended sign (including an abnormal laboratory finding), symptom, or disease temporally associated with the use of a medicinal (investigational) product, whether or not related to the medicinal (investigational) product. (ICH E6 (R2), 1.2)

**Serious adverse event (SAE) or serious suspected adverse reaction:** An AE or suspected adverse reaction is considered "serious" if, in the view of either the investigator or sponsor, it results in any of the following outcomes:

- death,
- a life-threatening adverse event,
- inpatient hospitalization or prolongation of existing hospitalization,
- a persistent or significant incapacity or substantial disruption of the ability to conduct normal life functions, or
- a congenital anomaly/birth defect.

Important medical events that may not result in death, be life-threatening, or require hospitalization may be considered serious when, based upon appropriate medical judgment, they may jeopardize the participant and may require medical or surgical intervention to prevent one of the outcomes listed in this definition. Examples of such medical events include allergic bronchospasm requiring intensive treatment in an emergency room or at home, blood dyscrasias or convulsions that do not result in inpatient hospitalization, or the development of drug dependency or drug abuse. (U.S. FDA 21 CFR 312.32(a))

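### Section 12.2 removes access and catheter events from AE status with no exception for serious ones, and is not reconciled with the SAE definition in Section 14 or with Table 2

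*Combined protocol and SAP*

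**What the plan says.** Section 12.2 starts AE collection on the procedure day, for enrolled subjects, and then lists three kinds of occurrence that do not count as AEs:

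- Conditions recorded as pre-existing, "unless there is a worsening of that condition in terms of nature, severity, or degree of incidence".
- Admissions arranged in advance, for an existing condition or because the protocol calls for a procedure, as long as health does not seriously worsen.
- Injuries from gaining access or placing the catheter, worded as "AEs arising from vascular access (e.g., hematoma, pseudoaneurysm, etc.), catheter selection (e.g., rupture, dissection, thrombosis").

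The first two carry a limit. The third carries none for seriousness, grade or relatedness.

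Section 12.1 sends the reader to Section 14 for AE definitions. There an AE is "Any untoward medical occurrence in a patient or clinical investigation subject administered a pharmaceutical product", with no causal link needed. An SAE is an AE, or suspected adverse reaction, with one of several outcomes, among them "inpatient hospitalization or prolongation of existing hospitalization". Neither definition excepts access or catheter events. Table 2 (Section 13.1.4) has the investigator report any SAE to the sponsor immediately.

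Section 9.4 opens with "An overall summary of severe adverse events (AEs, grade" 3 or higher) over the 24-hour period. It adds that "Serious adverse events (SAEs) will be summarized according to severity and relationship" and that "Complete subject listings of all site-reported AEs will be provided". It does not mention the exclusion in 12.2.

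**The concern.** The examples in the third bullet are not confined to minor events: rupture, dissection and thrombosis can each put a patient in hospital. A site faced with such an event in an infused subject would find one section calling it a non-AE, and two others that treat an event with that outcome as an SAE to be reported at once.

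Two things are at stake. The sponsor may not hear promptly of a serious event. And the SAE and grade 3 or higher counts in 9.4 may fall below what the Section 14 definitions would give, with nothing in 9.4 to warn the reader.

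**Working it through.** The plan gives no figure to reproduce here, so the main check sets the sections side by side.

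**Which events are in question.** Under Section 8.2 a patient is enrolled when any 99mTc-MAA is released. Section 12.2 collects AEs in enrolled subjects, and the Section 14 definition also presupposes that the product was given. Section 8.3 puts microcatheter selection before infusion. An access or catheter event that precedes release, or prevents it, is therefore outside AE collection whatever the third bullet says. What remains is events in infused subjects: for example, a thrombosis or pseudoaneurysm that appears during follow-up, or a dissection recognised only after infusion.

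**One such event, followed through both rules.** Take an infused subject admitted to hospital with a thrombosis arising from catheter selection.

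| Step | 12.2 governs | Section 14 governs |
|---|---|---|
| Is it an AE? | No | Yes |
| Is it an SAE? | No, since an SAE must first be an AE | Yes, by the hospitalization criterion |
| AE eCRF (12.2) | Not entered | Entered |
| Immediate report to sponsor (Table 2) | Not triggered | Required |
| SAE summary and listing (9.4) | Absent | Present |
| Grade 3 or higher summary (9.4) | Absent | Present if so graded under 12.4 |

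No section says which column applies. Section 12.3 does not settle it, because its duty to notify also starts from the event being an AE.

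**Other routes by which the event could surface.**

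- Section 13.1.3 keeps it in the case history.
- Section 13.7 has the IRB told of events likely to affect safety.
- Section 8.5 puts the reason for an early withdrawal on the Study Completion CRF.
- Section 13.6 has AE data fully checked against source, with a review for unreported AEs. A monitor who applies 12.2 would have no AE to query.

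None of these restores immediate SAE reporting to the sponsor or the counts in 9.4.

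**Size in the safety table.** The planned number of subjects is 5 (Section 7.2).

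- One serious event of grade 3 or higher, in a subject with no other: shown as 0/5 = 0%, against 1/5 = 20% under Section 14.
- If that event also causes withdrawal before 24 hours, the subject is replaced (8.5.1). Assuming that 9.4 uses all enrolled subjects, as 9.1 does for the primary analysis, n = 5 + 1 = 6. The table shows 0/6 = 0%, against 1/6 = 16.7%. The withdrawal form could then name the injury while 9.4 shows no SAE.

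**How likely it is.** The documents give no rate, so p per subject is assumed. P(none in 5) = (1 − p)^5.

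| Assumed p | P(none in 5) | P(at least one) |
|---|---|---|
| 0.5% | 0.995^5 = 97.5% | 2.5% |
| 1% | 0.99^5 = 95.1% | 4.9% |
| 2% | 0.98^5 = 90.4% | 9.6% |
| 5% | 0.95^5 = 77.4% | 22.6% |

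Where no event occurs, no reported count changes.

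**The case against.** The best defence is that 12.2 is a deliberate, study-specific narrowing of general definitions, and that narrowing is not contradiction. All three bullets narrow Section 14; a planned admission meets its hospitalization criterion, and the second bullet removes it. The rationale is also visible elsewhere. Subjects have the mapping procedure whether or not they enrol, Section 3.0 names SPECT/CT as the only study-specific procedure, and Section 11.2 leaves mapping risks to the site's own consent form.

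Much of this stands. Leaving out non-serious access events is a defensible choice, although 12.2 gives no reason for it. A reader might infer that the bullet contradicts the Section 14 AE definition as a whole; the documents do not support that, because a protocol may narrow a general definition. Nor does the bullet contradict Section 14 on grade, since Section 14 uses no grades; grade matters only for the 9.4 summary. Sections 12.1 and 12.5, which have relatedness to the mapping procedure rated, are not contradicted either, since other procedure-related events remain to be rated.

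The defence does not reach serious events in infused subjects. The two neighbouring bullets keep worsening or serious deterioration in; this one does not, and Table 2 admits no exception.

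It can also be said that a site might simply follow Table 2 and report. That is so, and the listing of site-reported AEs would then include the event. This makes the outcome uncertain, but it does not make the instruction clear.

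**Conclusion.** The point holds for serious access and catheter-selection events in infused subjects. Such an event is reportable under Section 14 and Table 2 and a non-AE under 12.2, and the protocol does not say which prevails.

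Two stronger readings might be inferred and are not supported. One is that the study will under-report serious events: that follows only if 12.2 is taken to override Section 14 and Table 2. The other is that every rupture or dissection at mapping, even a fatal one, is lost because of this bullet: those that precede or prevent release are outside AE collection already.

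The size is one subject in five, 20% shown as 0%, if such an event occurs and 12.2 is followed. The event is unlikely, at 2.5% to 22.6% for at least one among five under assumed rates that the documents do not supply. The dosimetry endpoints are not affected and no hypothesis is tested. The text should still be changed, because an investigator needs one clear reporting rule before a serious event happens.

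**What to change.** Reconcile 12.2 with Section 14 and Table 2:

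- Limit the third bullet of 12.2 to events that are not serious as Section 14 defines it. Serious access or catheter events in infused subjects then go on the AE eCRF and are reported under Table 2.
- Show them in 9.4 with a label that marks them as access/catheter events.
- State in 9.4 that non-serious access and catheter events are excluded, and why.

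Optionally, also keep non-serious events of grade 3 or higher in, to match the 9.4 summary threshold. Consistency with Section 14 does not require this.

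The cost is one limiting clause in 12.2, and one label and one sentence in 9.4. The downside is that an occasional event of a standard-of-care procedure appears in the safety table, separately labelled.

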### 12.3 Adverse Event Reporting Timeframes

The investigator is responsible for reporting SAEs to the IRB in accordance with the IRB's procedures.

- **Investigator Report:** If a subject experiences a reportable AE the investigator must notify the sponsor/CRO and the reviewing IRB immediately.
- **Postmarketing safety reports:** Applicants (individual or corporate entity that holds an NDA) are required to submit post-marketing safety reports to the FDA for human drug products with approved NDAs (§ 314.80).

## 12.4 Adverse Event Severity

The severity of an AE is a qualitative judgment of the degree of intensity, as determined by the investigator. The severity of the AE should be evaluated according to CTCAE v5.0. In the event a new version is released, this study will continue to use CTCAE v5.0. Refer to the severity of the AE – CTCAE displays Grades 1 through 5 with unique clinical descriptions of severity for each AE based on this general guideline.

- Grade 1: Mild; asymptomatic or mild symptoms; clinical or diagnostic observations only; intervention not indicated
- Grade 2: Moderate; minimal, local, or noninvasive intervention indicated; limiting age-appropriate instrumental Activities of Daily Living (ADL)
  - Instrumental ADL: Preparing meals, shopping for groceries and clothes, using the telephone, managing money, etc.
- Grade 3: Severe or medically significant but not immediately life-threatening; hospitalization or prolongation of hospitalization indicated; disabling; limiting self-care ADL
  - Self-Care ADL: Bathing, dressing and undressing, feeding self, using the toilet, taking medications, and not bedridden
- Grade 4: Life-threatening consequences; urgent intervention indicated
- Grade 5: Death related to AE

The assessment of severity should be made independent of the relatedness to the device and procedure or the seriousness of the event. CTCAE grading information is available at [https://ctep.cancer.gov/protocoldevelopment/electronic\\_applications/docs/CTCAE\\_v5\\_Quick\\_Reference\\_5x7.pdf](https://ctep.cancer.gov/protocoldevelopment/electronic_applications/docs/CTCAE_v5_Quick_Reference_5x7.pdf)

## 12.5 Adverse Event Relatedness

The investigator will assess the relatedness of the AE to 99mTc-MAA drug and the 99mTc-MAA mapping procedure using the categories listed below (see **Section 14.0** for definitions):

- Definitely
- Probably
- Possibly
- Unlikely
- Not Related

## 13.0 ADMINISTRATIVE PROCEDURES

### 13.1 Records & Reports

#### 13.1.1 Case Report Forms

Worksheets will be used to collect subject data that is not readily available from the source documentation. An electronic data capture (EDC) system will be used to collect study-required data on eCRFs. The principal investigator (PI) at the site is responsible for ensuring eCRFs are accurate and completed in a reasonable timeframe. The PI is required to review and approve the eCRF on the appropriate page(s) to verify the completeness, accuracy, and authenticity of the recorded data.

#### 13.1.2 Sponsor / CRO Study Records

The sponsor and CRO are responsible for maintaining study records and reports per applicable ICH Good Clinical Practices (GCP), FDA regulations, and applicable standard operating procedures and study-specific plans (e.g., Monitoring Plan, Data Management Plan, Training Plan, and Statistical Analysis Plan).

#### 13.1.3 Investigator Study Records

The investigator will securely maintain the following accurate, complete, and current records relating to their participation in the study as follows:

- All essential correspondence that pertains to the investigation.
- Records of each subject's case history and exposure to 99mTc-MAA during the study. Case histories include the CRFs and supporting data including, for example, signed and dated ICFs and medical records including, for example, progress notes of the physician, the individual's hospital chart(s), and the nurses' notes. Such records will include:
  - Documents evidencing the informed consent process. The case history of each subject will document that informed consent was obtained at the appropriate time.
  - All relevant observations, including records concerning AEs (whether anticipated or unanticipated), information and data on the condition of each subject upon entering, and during the course of, the investigation, including information about relevant previous medical history and the results of all diagnostic tests.
  - A record of the exposure of each subject to the 99mTc-MAA, including the date and time of use.
- The protocol, with documents showing the dates and reasons for each deviation from the protocol.
- Signed investigator agreements, financial disclosure agreements, investigator protocol signature pages, and curriculum vitae.
- IRB approval documents including approval of the protocol, protocol amendments, and ICF.

### 13.1.4 Investigator Reporting Requirements

Investigator reporting requirements are described in **Table 2** below.

**Table 2: Investigator Reporting Requirements**

Report	Submitted to	Description
Serious Adverse Events (SAE)	Sponsor/CRO & IRB	An investigator must immediately report to the sponsor any serious adverse event. Report to the IRB per IRB reporting requirements.
Serious and Unexpected Suspected Adverse Reaction	NDA holder	NDA holder of 99m Tc-MAA to submit postmarketing report to FDA (CFR 310.305, 314.80)
Withdrawal of IRB approval	Sponsor/CRO	Notification within 5 working days of withdrawal.
Progress Report	Sponsor/CRO & IRB	Periodic report detailing the progress of the study, occurring at least annually.
Deviations from protocol (CFR 812.150)	Sponsor/CRO & IRB	Emergency Use: Notification must be made within 5 working days of the occurrence of an emergency deviation (made to protect the life or physical well-being of a subject). Other: If the deviation affects scientific soundness of the study or the rights, safety, or welfare of the subject (and is not an emergency), prior approval must be obtained from sponsor the reviewing IRB, and FDA when required.
Failure to obtain informed consent	Sponsor/CRO & IRB	Notification within 5 working days
Final Report	IRB	Submitted within 3 months after termination or completion of the investigation.

